### **3.4 Timing of Outcome Assessments**

Outcomes measured at baseline, 3 months, and 6 months post-randomization.

# 4. Statistical Principles

#### 4.1 Confidence Intervals and P-Values

For the Prepare Romania trial, statistical analyses will be conducted with a two-sided significance level set at 0.05. This alpha level applies to all primary and secondary outcomes, ensuring that results are interpreted consistently across study endpoints. The 95% confidence intervals will be calculated for the primary and other key secondary outcomes.

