# 6. Analysis

#### **6.1 Outcome Definitions**

# **Primary Outcome**

The primary outcome of this study is PrEP adherence, which will be measured objectively using dried blood spot (DBS) testing to detect levels of tenofovir diphosphate (TFVdp). Adherence is defined as achieving a TFVdp concentration of ≥1000 fmol/punch, corresponding to a mean dosing frequency of at least four doses per week. This measure will be evaluated at 3- and 6-months post-randomization. The binary operationalization of this measure will serve as the primary outcome.

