#### 6.2 Analysis Methods

We will use Generalized Linear Mixed Models (GLMMs) to handle the various types of outcomes across primary and secondary measures, which allows for fixed effects (intervention, site, time, baseline outcome, the interaction between intervention and time baseline covariates) and random effects (including participant-level variability). The adjusted covariates include age, relationship status, and PrEP usage. All analyses will be conducted in R. The general form of the GLMM is:

$$g(\mu(Y_{ij})) = \beta_1 I(Time_{ij} = 3) + \beta_2 I(Time_{ij} = 3) \times Intervention + \beta_3 I(Time_{ij} = 6) + \beta_4 I(Time_{ij} = 6) \times Intervention + \beta_5 Covariates_i + \mu_i + \epsilon_{ij}$$

 $Y_{ij}$  represents the outcome for participant i at time j,  $\mu(Y_{ij})$  is the expected value of  $Y_{ij}$  given the covariates,

g(.) is the link function that relates the linear predictors to the expected value of outcome (e.g., logit link for binary outcomes, identity link for continuous outcomes),

 $\beta_1$  is the effect of time at 3 month,

 $\beta_2$  is the interaction effect between intervention and time at 3 month,

 $\beta_3$  is the effect of time at 6 month,

 $\beta_4$  is the interaction effect between intervention and time at 6 month,

 $\beta_5$  is the covariate effect,

 $\mu_i$  is the random intercept for each participant, where  $\mu_i \sim N(0, \sigma_i^2)$ ,

I(.) is the indicator function.

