### Treatment effects from the model

3 month	6 month
$eta_2$	$eta_4$

Then the average treatment effect is

$$\frac{\beta_2 + \beta_2}{2}$$

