# **Primary Outcome**

The primary outcome, PrEP adherence obtained through DBS, is a binary variable and will be analyzed using a GLMM with a logit link function. The intervention effect will be represented by an adjusted odds ratio, and will be assessed across different follow-up points. This analysis will be implemented in R using the "glmer()" function, specifying a logit link and a random intercept for participants to account for within-subject correlations.

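### The SAP does not say whether the 3-month, 6-month or average effect decides the primary outcome, and its printed formula for the average leaves out month 6

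*SAP*

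**What the plan says.** SAP 4.1 states that "statistical analyses will be conducted with a two-sided significance level set at 0.05" and continues: "This alpha level applies to all primary and secondary outcomes". It gives no split of alpha, no testing order and no adjustment.

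SAP 6.1 (Primary Outcome) dichotomises the DBS drug level and says: "The binary operationalization of this measure will serve as the primary outcome". On timing it says only: "This measure will be evaluated at 3- and 6-months post-randomization". Neither visit is ranked above the other.

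SAP 6.2 defines the contrasts:
- beta_2 "is the interaction effect between intervention and time at 3 month";
- beta_4 "is the interaction effect between intervention and time at 6 month";
- under the sub-heading on treatment effects from the model, "Then the average treatment effect is", followed by a formula printed as (beta_2 + beta_2)/2.

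The Primary Outcome paragraph of SAP 6.2 adds that the intervention effect, an adjusted odds ratio, "will be assessed across different follow-up points". The Secondary Outcomes paragraph says that each model reports effects by visit with 95% confidence intervals.

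The protocol does not settle the matter. Aim 1 and the Study Design section list the 3- and 6-month follow-ups side by side. The second hypothesis predicts better adherence without naming a time.

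**The concern.** The plan sets a significance level and one primary outcome, but it does not say which estimate the level applies to. A reader of the final report will ask whether the primary outcome was positive. As written, the answer could rest on 3 months, 6 months or the average, and the choice could be made after the results are seen. The SAP's Trial Design section describes the study as unmasked, so it is all the more important to fix the contrast in advance.

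The formula makes this worse. The average is the only quantity in the SAP that could serve as one summary of both visits, and as printed it contains nothing from month 6. An analyst who followed it literally would report the 3-month effect under the name of an average.

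**Working it through.** **Inputs from the SAP.** Two-sided alpha is 0.05 (4.1), so the critical value is 1.96. The contrasts are beta_2, beta_4 and their average (6.2).

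**Assumptions, not in the documents.** The correlation rho between the 3- and 6-month effect estimates is varied from 0 to 0.95. The two estimates have equal standard errors, and the test statistics are approximately normal.

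**Step 1: the plan's own figure.** For one contrast named in advance, P(|Z| > 1.96) = 0.05 under no effect. The stated level is reproduced.

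**Step 2: the formula as printed.** (beta_2 + beta_2)/2 = beta_2. Read literally, there are only two distinct effects. With beta_4 in place of the second beta_2 there are three.

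**Step 3: chance of at least one significant result under no effect.**
- Two visits: 1 − P(|Z3| < 1.96 and |Z6| < 1.96), from the bivariate normal distribution. At rho = 0 this is 1 − 0.95² = 9.75%.
- Three effects: the same with Z_avg = (Z3 + Z6)/√(2 + 2·rho) added, by simulation with 4 million draws.

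| Assumed rho | Two visits | Two visits and corrected average |
|---|---|---|
| 0 | 9.75% | 11.5% |
| 0.3 | 9.51% | 10.5% |
| 0.5 | 9.07% | 9.7% |
| 0.7 | 8.35% | 8.6% |
| 0.8 | 7.81% | 8.0% |
| 0.9 | 7.04% | 7.1% |
| 0.95 | 6.46% | 6.5% |

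Most of the excess over 5% comes from having two visits. For rho between 0.8 and 0.3 the average adds roughly 0.1 to 1.0 percentage points.

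**Step 4: direction.** The table counts significance in either direction. By symmetry, false results favouring the intervention are about half: 8.0%/2 = 4.0% at rho 0.8 and 10.5%/2 = 5.3% at rho 0.3, against a nominal 2.5%.

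**Step 5: effect of naming one contrast.** The error rate returns to 5% whichever contrast is named. If the average is named, its variance is (1 + rho)/2 of a single visit's under equal standard errors. At rho = 0.6 that is 1.6/2 = 0.80, or 20% less.

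**Step 6: the alternative of splitting alpha.** Testing each visit at 0.025 gives an overall rate of 3.3% to 4.9% for rho from 0.95 to 0. It costs power that the trial does not have. With 60 per arm and the planning rates in SAP 3.3, power is about 36% at 3 months (94% against 85%) and 18% at 6 months (92% against 86%) at the 0.05 level. At 0.025 it falls to about 26% and 12%.

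**The case against.** The strongest reply is that SAP 4.1 sets a level for each analysis and never promises control across contrasts. That stands. A reader might infer that the SAP's 5% is false; the documents do not support this, because each contrast taken alone does hold 5%. The excess arises only if any one of several may carry the claim.

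A reader might also infer that the plan commits to three separate tests, and quote the figure for three independent tests, 1 − 0.95³ = 14.3%. Neither follows. The SAP gives the average as a derived quantity and states no test for it. The average is also a function of the two visit effects, so independence cannot apply. The clear candidates are the two visits.

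The repeated beta_2 should not be read as a decision to disregard month 6. It looks like a typing error. In the extracted text the small table just above it has damaged symbols, so the duplicate may not even be in the source document. It needs checking there.

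The size depends on the assumptions. At rho of 0.9 or more the rate is only 6.5% to 7.1%. Normal tests are also approximate here: at the planning rates, 60 per arm implies between 60 × 0.06 = 3.6 and 60 × 0.15 = 9 non-adherent participants per arm at a visit.

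Lastly, SAP 3.3 calls the study an exploratory pilot without a formal power calculation, and the protocol speaks of early efficacy. This lowers the stakes but does not remove the point. The same SAP section claims sufficient power and a strong assessment of impact, and the SAP objective is to evaluate effectiveness.

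**Conclusion.** The point holds in a limited form. Neither document names the effect that decides the primary outcome. If any significant effect may count, the false-positive risk for that outcome as a whole exceeds 5% at every correlation below 1. The range in the brief rests on an assumed correlation, equal standard errors and approximate normality. The conclusion does not depend on how the formula is read, since two visits alone already exceed 5%. The printed average is wrong as it stands, unless the source document shows otherwise. The consequence is moderate: no confirmatory decision depends on this trial, but its result is meant to inform the design of a later one.

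**What to change.** 1. Check the formula under the treatment-effects sub-heading of SAP 6.2 against the source document, and correct it to (beta_2 + beta_4)/2.
2. State in SAP 4.1 and 6.1 which single contrast is the primary test at two-sided 0.05. The average is a reasonable default because the SAP already defines it and it uses both visits. The sponsor may prefer one visit and should then justify it. For example, the 6-point planning difference in SAP 3.3 is the 6-month one (92% − 86%), and the protocol's third hypothesis concerns use sustained over 6 months. Either choice holds 5%.
3. Report the remaining effects as odds ratios with 95% confidence intervals, labelled supportive, with no separate claim of success.

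The cost is SAP wording only. It needs no alpha split and no more participants. The sponsor gives up the freedom to claim success on whichever effect turns out significant.

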## **Secondary Outcomes**

The secondary outcomes include continuous DBS PrEP adherence, self-reported PrEP adherence (binary and continuous), PrEP knowledge (binary: all questions answered correctly vs. not), PrEP motivation (ordinal categorical), PrEP attitudes and beliefs (continuous), PrEP barriers, PrEP facilitators (continuous), PrEP stigma (continuous), anxiety symptomology (continuous), depression symptomology (continuous), STI diagnoses in the last 6 months (binary: any vs. none), and number of condomless anal sex (CAS) acts with HIV-positive or unknown-status partners in the last 6 months (continuous). For all secondary outcomes, missing data will be recorded and addressed.

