### **Secondary Outcomes**

The secondary outcomes include continuous, binary, and categorical variables, each analyzed with an appropriate link function based on the outcome type. For continuous outcomes, such as depression and anxiety symptomology scores, an identity link function will be used, estimating the intervention effect as the difference in mean scores between groups. This model will be implemented using the "lmer()" function in R. Binary secondary outcomes, will use the same logit link function and implementation details as the primary outcome analysis.

**Table 1.** List of secondary outcomes.

Variable coding
Continuous
Binary and continuous
Continuous
Continuous
Binary
Ordinal categorical, with 7 categories

PrEP stigma	Continuous
Positive attitudes/beliefs	Continuous
about PrEP	
Negative attitudes/beliefs	Continuous
about PrEP	
PrEP barriers	Continuous
PrEP facilitators	Continuous
STI diagnoses	Binary
CAS acts	Continuous

Each model will output the intervention effect at baseline, 3 months, and 6 months (with the exception of STI diagnoses and CAS acts, which are only measured at baseline and 6 months as well as DBS and self-report PrEP adherence, which are only measured at 3 months and 6 months), with 95% confidence intervals to provide estimates of precision.

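### SAP 4.1 gives every secondary outcome the primary's unadjusted two-sided 0.05 (14 analyses, 26 follow-up contrasts), with no order, adjustment or exploratory label

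*SAP*

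**What the plan says.** SAP 4.1 first fixes the level: "statistical analyses will be conducted with a two-sided significance level set at 0.05". It then gives the scope: "This alpha level applies to all primary and secondary outcomes, ensuring that results are interpreted consistently across study endpoints". On intervals it adds: "The 95% confidence intervals will be calculated for the primary and other key secondary outcomes". No secondary outcome is named as key anywhere in the SAP.

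SAP 6.1 separates one primary outcome from the rest. For DBS adherence it says: "The binary operationalization of this measure will serve as the primary outcome". The secondary list then begins: "The secondary outcomes include continuous DBS PrEP adherence, self-reported PrEP adherence (binary and continuous), PrEP knowledge", and goes on to motivation, attitudes, barriers, facilitators, stigma, anxiety, depression, STI diagnoses and CAS acts. Table 1 in SAP 6.2 splits attitudes into a positive scale and a second row, "Negative attitudes/beliefs".

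On what is reported for secondary outcomes, SAP 6.2 says: "Each model will output the intervention effect at baseline, 3 months, and 6 months". The same sentence exempts STI diagnoses and CAS acts from the 3-month visit and the adherence measures from baseline. It ends by promising 95% confidence intervals.

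**The concern.** This is a stated rule, not a silence on multiplicity. The SAP takes care to name one primary outcome, and 4.1 then applies the same unadjusted test to every secondary outcome so that all are read alike. Nothing in the plan tells a reader how to treat a significant secondary result when the primary is null.

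That situation is easy to picture here. Three secondary analyses (continuous DBS, and self-reported adherence in binary and continuous form) measure the same construct as the primary. A null result on binary DBS could sit beside a significant result on one of their six follow-up contrasts, and the plan as written would let that be reported as a finding at the 0.05 level. The trial is meant to inform a larger one (SAP 3.3; Protocol, Aim 2), so a chance result could influence that trial's choice of outcomes.

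**Working it through.** **The plan's own figure.** On multiplicity the SAP gives only the per-test level, two-sided 0.05, which is 0.025 in the direction of benefit. It states no family-wise rate, so there is none to reproduce.

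**Counting the analyses** (SAP 6.1 and Table 1 in 6.2): continuous DBS; self-report binary; self-report continuous; knowledge; motivation; positive attitudes; negative attitudes; barriers; facilitators; stigma; anxiety; depression; STI; CAS. That is 14, or 13 if attitudes are counted once as in 6.1.

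**Counting the contrasts** (visit rules in SAP 6.2): 12 outcomes × 2 visits + 2 outcomes × 1 visit = 26. Baseline contrasts and the two-visit average effect are left out. The secondary-outcome text lists only per-visit effects.

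**Independent tests, no true effect.** The chance of at least one false result is 1 − (1 − α)^k.
- 26 contrasts, either direction: 1 − 0.95^26 = 0.736. Benefit only: 1 − 0.975^26 = 0.482.
- 14 contrasts (6 months only), either direction: 1 − 0.95^14 = 0.512. Benefit only: 1 − 0.975^14 = 0.298.
- Expected number of false results among 26: 26 × 0.05 = 1.3 in either direction, and 26 × 0.025 = 0.65 for benefit. Correlation does not change these two figures.

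**Correlated tests.** Related scales measured twice in the same men are not independent, so the rates were also simulated. The test statistics were normal with no effect and at least 200,000 draws per setting. The correlation is r between outcomes at one visit, t between visits for one outcome, and r × t otherwise. All outcomes are oriented so that positive means benefit. A result counts as significant if |z| > 1.96, or as benefit if z > 1.96. The documents give neither r nor t, so both are assumptions.

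| r | t | 26 contrasts, either direction | 26 contrasts, benefit | 14 at 6 months, either direction | 14 at 6 months, benefit |
|---|---|---|---|---|---|
| 0 | 0.5 | 0.712 | 0.457 | 0.513 | 0.300 |
| 0.3 | 0.5 | 0.635 | 0.346 | 0.439 | 0.225 |
| 0.5 | 0.5 | 0.529 | 0.274 | 0.348 | 0.174 |
| 0.8 | 0.8 | 0.282 | 0.141 | 0.199 | 0.099 |

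**The three secondary adherence measures** (3 × 2 = 6 contrasts), at r = t = 0.5: about 22% in either direction (range 15% to 25%) and about 11% for benefit (range 7% to 13%).

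**The case against.** The best defence is that this is a pilot with one named primary outcome. SAP 3.3 speaks of preliminary data and an exploratory study, and the protocol calls the trial a pilot of early efficacy. Many trials report secondary outcomes unadjusted, and the SAP makes no family-wise claim that they could breach. Much of this stands, and it limits the point in five ways.

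- A reader might infer that a false secondary *benefit* is about as likely as not. The 53% counts results in either direction, including apparent harm. The benefit figure at the same correlations is 27%, and even full independence gives 48%.
- A reader might infer that all 14 analyses are tested at both visits. SAP 6.2 gives STI diagnoses and CAS acts no 3-month measurement, so the count is 26 and not 28.
- A reader might infer that the undefined key secondary outcomes could be picked after the results are seen. SAP 6.2 already promises 95% intervals from each model, so that wording in 4.1 is loose but gives little room for selection.
- A reader might set 53% against the 5% in 4.1 as an inflation of a stated error rate. The 5% is a per-test level, so the two are different quantities.
- A reader might infer that secondary outcomes carry the same evidential weight as the primary. SAP 6.1 still names one primary outcome, and a null primary would remain null.

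The pilot defence does not dispose of the point. SAP 3.3 uses the exploratory label only to explain why no power calculation was done, and the same section goes on to speak of adequate power and a robust assessment. SAP 2.2 and 3.1 describe an evaluation of effectiveness. SAP 4.1, which governs interpretation, carries no such label. Secondary outcomes need no family-wise control if they are declared exploratory, but the plan does not declare it.

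**Conclusion.** The concern holds in this limited form. SAP 4.1 applies an unadjusted two-sided 0.05 to 14 secondary analyses with 26 follow-up contrasts, to be read consistently with the primary, and no order, adjustment or exploratory status is given for them. With no true effect, the chance of at least one false significant secondary result is about 53% in either direction (28% to 71%) and about 27% for benefit (14% to about 45%).

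The central figures assume correlations of 0.5 between outcomes and 0.5 between visits. The ranges run from 0.8 for both to independent outcomes with 0.5 between visits. They illustrate how often chance alone would produce something to report; they do not show that the plan breaks a promise it made. The point concerns the secondary outcomes only, not the primary's two visits. It is worth acting on because it affects what the trial may conclude and costs almost nothing to settle.

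**What to change.** In SAP 4.1, replace the sentence that extends the alpha level to all outcomes with:

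> The two-sided 0.05 significance level applies to the primary outcome. Secondary outcomes are exploratory: they are reported for every listed outcome and measured visit as estimates with 95% confidence intervals not adjusted for multiplicity, and will not be used to claim efficacy.

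In the interval sentence of 4.1, change the reference to other key secondary outcomes to all secondary outcomes, so that it agrees with SAP 6.2.

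This needs no new data and no new analyses. The price is that the sponsor gives up unadjusted significance claims for secondary outcomes. A formal adjustment such as Holm's method across the 14 analyses is not needed. It would start at 0.05/14 = 0.0036 per test with 60 per arm, a trade-off that only matters if the sponsor wants to keep significance claims for secondary outcomes.

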# **4.2** Analysis Populations

The primary analysis for the Prepare Romania trial will follow the intention-to-treat (ITT) principle.

# **4.3 Baseline Patient Characteristics**

Baseline characteristics will be summarized with descriptive statistics, including study site, age, sexual identity, outness, relationship status, high school location, ethnicity, education level, occupation, income, previous PrEP usage, and current PrEP status.

To assess baseline balance between the groups, we will calculate the Absolute Standardized Difference (ASD) for each characteristic.

# 6. Analysis

#### **6.1 Outcome Definitions**

# **Primary Outcome**

The primary outcome of this study is PrEP adherence, which will be measured objectively using dried blood spot (DBS) testing to detect levels of tenofovir diphosphate (TFVdp). Adherence is defined as achieving a TFVdp concentration of ≥1000 fmol/punch, corresponding to a mean dosing frequency of at least four doses per week. This measure will be evaluated at 3- and 6-months post-randomization. The binary operationalization of this measure will serve as the primary outcome.

## **Secondary Outcomes**

The secondary outcomes include continuous DBS PrEP adherence, self-reported PrEP adherence (binary and continuous), PrEP knowledge (binary: all questions answered correctly vs. not), PrEP motivation (ordinal categorical), PrEP attitudes and beliefs (continuous), PrEP barriers, PrEP facilitators (continuous), PrEP stigma (continuous), anxiety symptomology (continuous), depression symptomology (continuous), STI diagnoses in the last 6 months (binary: any vs. none), and number of condomless anal sex (CAS) acts with HIV-positive or unknown-status partners in the last 6 months (continuous). For all secondary outcomes, missing data will be recorded and addressed.

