Control Arm (Prep Education Condition): Participants randomized to the control arm will not meet with the Prep counselor or have access to the app. They will only meet with the study IDP, who will deliver Prep education. This education content is based on previously tested Prep messaging education protocol. The low Prep knowledge among Romanian GBM suggests the utility of a comprehensive Prep education intervention. The IDPs (not Prep counselors) will deliver this condition and be instructed to follow it as scripted using check-lists, as to avoid cross-arm contamination. The IDP will first review lab test results and then provide basic Prep information: what it is (e.g., definition), how it works (e.g., prevents virus replication), efficacy (e.g., clinical trials evidence), side effects (e.g., type, duration), and importance of daily use (e.g., to build and sustain protective levels), and continued condom use (e.g., Prep as an added layer of protection against HIV, but not STIs, unless condoms are used). IDPs will answer questions and provide Prep brochures. Participants will return 3 an 6 months after the first visit, as described below. Follow-up Visits. Participants in both arms will receive a Prep prescription to be filled at

the co-located pharmacy and schedule a follow-up visit 3 months later. At that visit, participants will meet with their counselor and/or IDP to review past-3-month PrEP use, side effects, clarify questions, conduct biological testing as above, and receive a PrEP refill if desired. The same procedures will be used at the 6-month follow-up. Retention. For high app-based engagement and retention follow-up, we will apply strategies we have utilized across our NIH-funded interventions, two of which entailed 8 mHealth counseling sessions with >82% completion and 86% and 93% retention at 3- & 24-months. Study engagement will be bolstered by our GBM-affirmative research staff who will routinely verify and use participants' multiple means of communication (phone calls, SMS, multiple social media messaging, alternate contacts). PrEP counselors will contact unresponsive participants. Participants will be compensated \$30, \$35 & \$40 for BL, 3M, and 6M surveys, and \$30 for exit interviews (20% randomly selected).

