# 3. Study Methods

### 3.1 Trial Design

The Prepare Romania trial is a two-arm, parallel-group randomized controlled trial (RCT) with a 1:1 allocation ratio, designed to evaluate the effectiveness of a culturally adapted intervention to improve adherence to PrEP among GBMSM in Romania. Participants are randomized to either the intervention or control arm. The intervention arm includes a combination of counseling and a culturally tailored mobile health app that supports PrEP adherence. Participants in the control arm receive standard PrEP education only. Randomization is stratified by city (Bucharest and Cluj-Napoca), and the study is unmasked, with both participants and staff aware of group assignments. Primary and secondary outcomes will be collected at baseline, 3 months, and 6 months post-randomization.

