# 3.3 Sample Size

The Prepare Romania trial's sample size was chosen to provide preliminary data on the hypothesized intervention outcomes, PrEP adherence and persistence among GBMSM in Romania, as well as to inform the design of a future effectiveness trial. A formal power calculation was not conducted due to the exploratory nature of this pilot study. Instead, we followed guidance from Whitehead et al., which provides recommendations for sample sizes in pilot studies.

The sample size of 60 participants per arm (120 total) was selected based on conservative effect size estimates drawn from previous studies evaluating PrEP adherence interventions. In a comparable RCT testing the SPARK intervention, protective PrEP levels (defined as adherence of ≥4 doses per week) were observed in 94% of the intervention arm and 85% of the control arm at the 3-month follow-up, with corresponding rates of 92% and 86% at 6 months. This difference in adherence rates translates to an estimated effect size of 6%, with a pooled standard deviation of approximately 0.32, yielding a standardized effect size of 0.19. Whitehead et al. suggest a minimum sample size of 25 participants per condition for pilot trials when the effect size falls between 0.1 and 0.3. To ensure adequate power, the Prepare Romania trial conservatively enrolls 60 participants per arm, exceeding this minimum and allowing for a robust assessment of intervention impact.

Each site (Bucharest and Cluj-Napoca) is tasked with recruiting 60 participants. With this sample size, the study expects retention at 6 months to exceed 25 participants per arm, even accounting for potential attrition. This estimate is supported by high retention rates (approximately 89%) reported in prior SPARK trials.

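### PrEP knowledge is analysed only as all questions correct versus not, which ignores partial gains and usually costs power; the number correct should be analysed beside it

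*SAP*

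**What the plan says.** The Secondary Outcomes list in SAP 6.1 gives the coding as "PrEP knowledge (binary: all questions answered correctly vs. not". Table 1 is only partly legible, but its coding column has a binary entry consistent with this. For the model, SAP 6.2 states: "Binary secondary outcomes, will use the same logit link function and implementation details as the primary outcome analysis". That means a logit link with a participant random intercept. The baseline value of the outcome is among the fixed effects in 6.2. Knowledge is not among the exceptions listed under Table 1, so it is expected at baseline, 3 months and 6 months.

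The same list in 6.1 treats adherence differently: "self-reported PrEP adherence (binary and continuous", and blood-spot adherence is likewise analysed in binary form (primary) and continuous form (secondary). Attitudes, facilitators, stigma, anxiety and depression are continuous, and motivation is ordinal.

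On size and testing: "The sample size of 60 participants per arm (120 total" (SAP 3.3), "two-arm, parallel-group randomized controlled trial (RCT) with a 1:1 allocation ratio" (SAP 3.1), and "statistical analyses will be conducted with a two-sided significance level set at 0.05" (SAP 4.1). SAP 3.3 adds: "A formal power calculation was not conducted due to the exploratory nature of this pilot study".

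**The concern.** An all-or-none cut treats every score below perfect as the same. A man who moves from two right answers to all but one is recorded as unchanged, and the dichotomised baseline separates participants less well than their scores would. The blood-spot cut-off is tied in SAP 6.1 to a dosing frequency. The knowledge cut has no comparable justification.

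The protocol's Study Purpose and Rationale names knowledge as one of the means by which the programme acts. Both arms receive PrEP teaching from the infectious disease physician, so the difference between arms may well be incremental, which is the kind of difference this coding can miss. If perfect scores are rare, the logistic mixed model also rests on few events. The pilot is meant to inform a later trial, and a mean score with its SD is more useful for that than an odds ratio from sparse data.

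**Working it through.** **The plan's own figure.** The only effect size in the SAP concerns adherence: 0.06 / 0.32 = 0.19. From 92% versus 86%, SD = √[(0.92×0.08 + 0.86×0.14)/2] = 0.311 and 0.06/0.311 = 0.19, so it reproduces. It says nothing about knowledge, for which no figure is given.

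**Inputs.** From the SAP: 60 per arm, 1:1, two-sided 0.05, and retention of about 89% (0.89 × 60 ≈ 53 per arm). Assumed, because the documents are silent: 5% to 50% of controls all-correct, a score effect of 0.2 to 0.8 SD, 5 to 15 items, 60% to 90% mean correct, and inter-item correlation 0 to 0.4.

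**Check 1: latent normal score cut at the all-correct threshold.** With control share p and c = Φ⁻¹(1−p), the relative efficiency of binary to score is φ(c)²/[p(1−p)]. For p = 0.10, c = 1.282, φ(c) = 0.1755, and 0.0308/0.09 = 0.34. An effect of 0.5 SD moves the all-correct share to 1−Φ(1.282−0.5) = 21.7%. At 60 per arm, 10% versus 21.7% has 42% power, against 78% for the score.

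| Controls all-correct | Relative efficiency | Binary power, 0.5 SD (score 78%) | Binary/score power ratio, 0.2–0.5 SD |
|---|---|---|---|
| 50% | 0.64 | 57% | 0.67–0.73 |
| 30% | 0.58 | 57% | 0.65–0.73 |
| 20% | 0.49 | 53% | 0.59–0.67 |
| 10% | 0.34 | 42% | 0.46–0.54 |
| 5% | 0.22 | 31% | 0.35–0.41 |

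For an effect of 0.8 SD the ratio is 0.71–0.94. Results at 53 per arm are nearly the same. Efficiency and power must not be equated: at 20% all-correct the effective sample size halves, but power falls by about 33% to 41%. At 10% all-correct there are 0.10 × 60 = 6 control events per visit, and at 5% there are 3.

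**Check 2: beta-binomial number correct, 53 per arm, effect set so that the score has 80% power.**

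| Items | Control mean correct | Inter-item correlation | All-correct, control vs intervention | Binary power |
|---|---|---|---|---|
| 10 | 75% | 0 | 5.6% vs 13.8% | 29% |
| 5 | 60% | 0 | 7.8% vs 18.7% | 38% |
| 5 | 75% | 0 | 23.7% vs 43.6% | 58% |
| 10 | 90% | 0 | 34.9% vs 57.3% | 64% |
| 10 | 75% | 0.2 | 23.1% vs 46.1% | 71% |
| 10 | 90% | 0.2 | 57.3% vs 85.0% | 89% (no loss) |

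**Check 3: item-response simulation with baseline adjustment.** 60 per arm, one follow-up, latent log-odds effect 0.5, ability SD 1, baseline-to-follow-up correlation 0.6, item difficulties from −1 to 1. Power, binary versus number correct:

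- Controls about 68% correct: 26% vs 48% (5 items), 21% vs 63% (10), 9% vs 67% (15). Relative losses, (score − binary)/score: 46%, 67%, 87%.
- Controls about 83% correct: 26% vs 33%, 30% vs 52%, 26% vs 58%. Losses 21%, 42%, 55%.
- Low baseline (50% correct) but about 92% correct in controls after education: 20% vs 22% (5 items), 26% vs 37% (10), 28% vs 41% (15). Losses 9%, 30%, 32%. With 3 items there is no loss (20% vs 19%).

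All three checks use a single follow-up. None fits the planned mixed model with multiple imputation, so they show direction and range, not the trial's power.

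**The case against.** A reader might infer that the cut discards most of the information and halves power. The documents do not support that as a statement about this trial. It needs an item count, score distribution and effect that they do not give. Only three of the six lower- and higher-knowledge cases in check 3 lose half, and check 2 has a case with no loss.

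A reader might also infer that perfect scores will be rare, because the protocol's control-arm text says: "The low Prep knowledge among Romanian GBM suggests the utility of a comprehensive Prep education intervention". That sentence is the reason for teaching. Controls then receive scripted education, and physicians reinforce PrEP facts in the intervention arm, all before the 3- and 6-month assessments. SAP 4.3 also lists previous and current PrEP use among the baseline characteristics, so some participants may already know a good deal. Low knowledge beforehand does not establish few events at follow-up.

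Three further points stand. Knowledge is not the only non-continuous questionnaire measure, since motivation is ordinal. Full mastery is a readable endpoint with some value of its own. Replacing it outright by a linear model is not clearly safe for a bounded score of unknown length. The consequence is also limited: knowledge is in none of the protocol's three hypotheses, and the mediators named under Aim 1 are self-efficacy and mental health.

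None of this supplies a reason for having the all-correct analysis alone.

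**Conclusion.** The concern holds as a modest one. Coding knowledge only as all-correct ignores partial gains, coarsens the baseline covariate and usually loses power. Under the assumed values the loss runs in three bands:

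- none, with easy, correlated items near the ceiling;
- roughly 25% to 40% of power, with 20% to 50% of controls all-correct and effects up to 0.5 SD;
- about half or more, with about 10% or fewer all-correct and a small to moderate effect, or with many weakly correlated items.

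The documents do not show which band applies. That the number correct can be recovered is an inference: the all-correct flag has to be derived from answers to more than one question, but the instrument is not described. For one secondary outcome in an exploratory pilot, this is a worthwhile improvement and does not affect the primary analysis.

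**What to change.** In SAP 6.1 and Table 1, state the number of knowledge items. Pre-specify the number of correct answers, adjusted for the baseline number correct, as the main knowledge analysis, using the linear mixed model already planned for continuous outcomes. Name in advance an ordinal or binomial form to be used if there are few items or a ceiling. Keep the all-correct share alongside it, as the SAP already does with the two forms of adherence, and give the reason for that cut.

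The cost is a line or two of text and one more secondary analysis, and no new data if item answers are stored. The effect becomes a difference in mean score under the linear model, slightly less simple to state than a percentage.
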